6. SPECIFIC AIMS

Aim 1: To compare the symptoms of PLWH+OSA vs. PLWH–OSA. This aim will allow us to test the hypothesis that fatigue is overexpressed in PLWH+OSA compared to PLWH–OSA, independent of known covariates. We will develop a multivariate model to predict fatigue based on clinical accessible data.

Aim 2: In those PLWH found to have OSA, we will:

a. Compare neurocognitive performance [psychomotor vigilance test (primary outcome), NIH Toolbox Cognition] in PLWH+OSA with low arousal threshold vs. those with a high arousal threshold. We hypothesize that stratified for similar disease severity, low arousal threshold induced OSA yields worse neurocognitive dysfunction compared to equal severity OSA with high arousal threshold.

b. Compare endothelial function (arterial tonometry) in PLWH+OSA with high loop gain (ventilatory instability with associated hypoxemia/hypercapnia) vs. those with low LG, to test the hypothesis that stratified for similar disease severity, LG-induced OSA yields worse endothelial function compared to equal severity OSA with low LG.

Aim 3: To test in PLWH+OSA whether 3 months of PAP treatment results in changes in OSA manifestations. This aim will allow us to test the hypothesis that endotype underlying OSA will be predictive of the specific clinical improvements seen in adherent users of PAP therapy. For example, those with high LG at baseline will have the greatest improvement in endothelial dysfunction with PAP therapy compared to other OSA patients with similar disease severity as measured by AHI.

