OSA is a multifactorial disease with different manifestations – Endotypes and Phenotypes: OSA is increasingly recognized as a multifactorial disorder i.e., different people have OSA for different reasons. Although an anatomical predisposition (collapsibility of the upper airway) is generally required, other factors are important as well, including a low respiratory arousal threshold (wake up too easily), dysfunction in upper airway dilator muscles and instability in ventilatory control (which we quantify using the engineering term loop gain [LG]) which leads to periods of decreased pharyngeal tone.⁴⁰ The ultimate goal of our work is to personalize therapy for OSA one day by addressing the underlying endotype to treat OSA effectively in an individual with targeted therapy.⁴¹

Different patients with OSA may also have different symptoms, and variable risk of certain co-morbidities. That is, two patients of the same gender, weight and OSA severity, as defined by the apnea-hypopnea index (AHI), may have very different observable consequences of OSA, or phenotypes. The concept of OSA phenotypes has been advanced by multiple groups. For example, Ye and colleagues found 3 distinct clusters of OSA types based on sleep questionnaire responses, which they labelled the “disturbed sleep”, “minimally symptomatic”, and “excessive daytime sleepiness” groups.⁴² The clusters did not differ based on sex, BMI, or sleep apnea severity. However, the clusters did vary in associations with hypertension and cardiovascular disease, a finding consistent with other studies.^{43,44} Although AHI is frequently used to assess OSA severity, AHI does not correlate strongly with most relevant OSA co-morbidities.^{45,46} A related observation is that while treatment of CPAP can improve blood pressure, the effect is highly variable across individuals.⁴⁷ Taken together, these observations suggest that the expression of OSA in an individual is often variable.

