Statistical Analysis Plan: First, we will evaluate if there is a difference in the primary outcome, FACIT-F scores, between OSA and non-OSA participants using a two-sample t-test. Multiple regression modeling will be used to assess the association between FACIT-F scores and OSA status (dichotomous independent variable), adjusting for other potential covariates, such as age, OSA severity (AHI), medications, mean sleep duration as assessed by actigraphy, and inflammation as assessed by CRP or similar such as IL-6.

Aim 2 – OSA Endotyping

Data Analysis: From the research PSG, the upper airway collapsibility as defined by the critical closing pressure (Pcrit) will be analyzed according to published methods. Additionally, the relevant traits will be extracted with the aid of MATLAB (Natick, MA) and our custom software. The traits will then be plotted on the axes ventilation vs. ventilatory demand to produce an individual assessment of the relevant traits for each subject

Aim 2: In those PLWH found to have OSA, we will perform detailed physiological assessments to determine endotype. This aim will allow us to test the following hypotheses:

Hypothesis 2A: To compare neurocognitive performance (PVT) in PLWH+OSA with a low arousal threshold (wake up too easily) vs. those with a high arousal threshold. This aim will allow us to test mechanistically the hypothesis that stratified for similar disease

severity, low arousal threshold induced OSA yields worse neurocognitive dysfunction compared to equal severity OSA with high arousal threshold.

Hypothesis 2B: To compare endothelial dysfunction via arterial tonometry in PLWH and OSA with a high loop gain (ventilatory instability with associated hypoxemia/hypercapnia) vs. those with low LG. This aim will allow us to test the hypothesis that stratified for similar disease severity, LG-induced OSA yields worse endothelial function compared to equal severity OSA with low LG.

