Sample Size Justification: Of the 120 PLWH studied in Aim 1, we believe that at least 60 will have OSA. We will split the cohort of those with OSA into high and low arousal threshold at the median value for the group. Although we will have multiple markers of cognitive function, our main outcome for Aim 2A for statistical purposes will be the psychomotor vigilance test (PVT). Prior work by Kribbs and colleagues reported a mean reciprocal reaction time of 3.9 seconds⁻¹ with a standard deviation of 0.5 (Ref 112). We believe that a change of 0.3 seconds⁻¹ represents a clinically important difference based on the effect size of CPAP observed with prior studies (Ref 123). Therefore, assuming a mean reciprocal reaction time of 3.9 seconds⁻¹ in those with low arousal threshold OSA and 4.2 seconds⁻¹ in those with high arousal threshold OSA, and a SD of 0.5 in both groups, we will have adequate power (beta >0.8) to detect a difference between the two groups (alpha = 0.05).

Statistical Analysis Plan: We will evaluate if there is a difference in PVT in OSA participants with low vs high AT using a two-sample t-test. As a sensitivity analysis, we will consider multiple regression models adjusting for additional covariates such as age, AHI, medications, mean sleep duration via actigraphy, and inflammation as assessed by CRP or IL-6 may be included in the modeling if significantly associated with outcome (p<0.10).

Aim 3 – Impact of OSA treatment on Sleep and Activity Phenotypes

To test in PLWH+OSA whether 3 months of PAP treatment results in changes in OSA manifestations. This aim will allow us to test the hypothesis that endotype underlying OSA will be predictive of the specific clinical improvements seen in adherent users of PAP therapy. For example, those with high LG at baseline will have the greatest improvement in endothelial dysfunction with PAP therapy compared to other OSA patients with similar disease severity as measured by AHI.

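### Hypothesis 2A is stated at equal OSA severity, but its main test is an unadjusted t-test between halves split on arousal threshold alone

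*SAP*

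**What the plan says.** **Hypothesis.** Protocol section 6 (Aim 2a): "We hypothesize that stratified for similar disease severity, low arousal threshold induced OSA yields worse neurocognitive dysfunction". The SAP's Hypothesis 2A repeats this, conditioning on similar disease "severity, low arousal threshold induced OSA yields worse neurocognitive dysfunction compared to equal severity OSA with high arousal threshold". Equal severity is part of the question in both documents.

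**Groups.** SAP, Aim 2, Sample Size Justification: "We will split the cohort of those with OSA into high and low arousal threshold at the median value for the group".

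**Main test.** SAP, Aim 2, Statistical Analysis Plan: "We will evaluate if there is a difference in PVT in OSA participants with low vs high AT using a two-sample t-test".

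**Where AHI comes in.** The next sentence of the SAP offers multiple regression as a sensitivity analysis to be considered, naming AHI as one of several example covariates. It ends by saying that covariates "may be included in the modeling if significantly associated with outcome (p<0.10" (closing bracket omitted). The sentence does not parse. AHI may be adjusted for outright, or only if it passes the 0.10 screen.

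**How the plan measures severity.** The SAP's Aim 3 hypothesis speaks of improvement "compared to other OSA patients with similar disease severity as measured by AHI". In Aim 1, a regression follows the t-test as a firm commitment, "adjusting for other potential covariates, such as age, OSA severity (AHI), medications" and others.

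**The concern.** A median split on arousal threshold does nothing to balance AHI between the halves. Eligibility does not balance it either, because OSA is any AHI above 5/h with no upper limit (Protocol section 9; SAP, Aim 1). Neither document defines severity strata, matching or any other way to carry out the stratification that the hypothesis names.

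If the halves differ in AHI and AHI is related to PVT, the t-test mixes a severity difference with an arousal-threshold difference. It could then show an effect that is absent at equal severity, or hide one that is present. The analysis that could address this is optional, and the SAP does not say which result answers Hypothesis 2A if the two disagree.

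**Working it through.** **1. The plan's own figure.** SAP inputs: 60 people with OSA, so 30 per half; means 3.9 and 4.2 s⁻¹; SD 0.5; alpha 0.05; stated power above 0.8.

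- SE = 0.5 × √(2/30) = 0.129, so the noncentrality is 0.3/0.129 = 2.32.
- Two-sided power is 0.628 by the t distribution (58 df) and 0.642 by the normal. One-sided, it is 0.743 and 0.751.
- The stated figure does not reproduce; 80% two-sided power needs 45 per half (90 in all). This is a separate point, but it is the baseline for costing any change.

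**2. Bias from leaving AHI out.** Let ρ be the correlation of arousal threshold with AHI, and b the effect of one SD of AHI on PVT in SD units. The documents give neither, so both are assumed. Under normality, a median split separates the halves by 2√(2/π)·ρ SDs of AHI, so

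bias = 2√(2/π) × ρ × b × 0.5 s⁻¹ = 0.798 × ρ × b.

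Rejection rates below are for no arousal-threshold effect at equal AHI (simulation, N=60, 20,000 runs per row).

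| ρ | b | Bias (s⁻¹) | Share of 0.3 | Rejects, unadjusted | Rejects, AHI always in |
|---|---|---|---|---|---|
| 0.3 | 0.2 | 0.048 | 16% | 0.067 | 0.052 |
| 0.3 | 0.4 | 0.096 | 32% | 0.110 | 0.050 |
| 0.5 | 0.2 | 0.080 | 27% | 0.092 | 0.050 |
| 0.5 | 0.4 | 0.160 | 53% | 0.228 | 0.048 |

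Weaker links shrink this quickly. At ρ=0.1, b=0.2 the bias is 0.016 (5% of 0.3); at ρ=0.3, b=0.1 it is 0.024 (8%). Rejection is then between 5% and 6%.

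**3. Opposing effects and the p<0.10 screen.** True difference 0.3 at equal AHI, with the AHI effect in the other direction. The screen here tests AHI against PVT alone.

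| ρ | b | Mean estimate: unadjusted / screened / AHI always in | Power: screened / AHI always in |
|---|---|---|---|
| 0.3 | −0.2 | 0.253 / 0.270 / 0.300 | 0.544 / 0.616 |
| 0.3 | −0.4 | 0.206 / 0.288 / 0.300 | 0.639 / 0.669 |
| 0.5 | −0.2 | 0.220 / 0.240 / 0.299 | 0.445 / 0.561 |
| 0.5 | −0.4 | 0.142 / 0.267 / 0.299 | 0.537 / 0.620 |

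With 60 people, the screen admits AHI only if its observed correlation with PVT is about 0.21 or more. With no arousal-threshold effect, this screen keeps rejection near 5%. If AHI is instead screened with group already in the model, rejection reaches about 8% (ρ=0.5, b=0.2).

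**4. Cost of always including AHI.**

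- Variance inflation = 1/(1 − (ρ√(2/π))²): 1.061 at ρ=0.3 and 1.189 at ρ=0.5.
- Residual variance = 0.25(1 − b²), with 57 df.

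| ρ | b | Power at N=60 | N for 0.80 |
|---|---|---|---|
| 0.3 | 0.2 | 0.619 | 92 |
| 0.3 | 0.4 | 0.677 | 80 |
| 0.5 | 0.2 | 0.571 | 102 |
| 0.5 | 0.4 | 0.628 | 90 |

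The unadjusted test has 0.628 at N=60 and needs 90.

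**The case against.** **A severity analysis is already there.** The SAP lists AHI in the Aim 2A sensitivity regression, and on one reading adjusts for it outright. Even under the screen, an AHI effect of 0.4 SD with no arousal-threshold effect passes in about 94% of simulated trials, so the worst false-positive figures would be caught there. This is true. The fault is which analysis is the main one, not that AHI is absent. But the regression is optional and would not be the headline result.

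**The size is assumed.** The protocol's Background says "AHI does not correlate strongly with most relevant OSA co-morbidities", which favours the lower end of the range or values below it. This stands. The figures illustrate the mechanism and do not estimate the bias in this trial. The mismatch between hypothesis and test does not depend on them.

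**AHI may not be a confounder.** The Background lists a low arousal threshold among several causes of OSA, so AHI may be a consequence of it. AHI may also be a shared consequence of the other traits, and conditioning on it can then link arousal threshold to those traits. The simulation treats AHI as an ordinary linear covariate and does not show this. The caveat limits a causal reading of the adjusted estimate. It does not rescue the t-test, because the case for adjusting is that the hypothesis conditions on severity. An unadjusted comparison would be a legitimate choice, but for a different hypothesis.

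**Aim 1 is a weak model.** It also starts from a t-test, names AHI only as an example, and has OSA status defined by AHI. Agreed; it shows only that the SAP commits to regression there and not in Aim 2A.

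**Conclusion.** The concern holds. As written, the main Aim 2A result does not condition on severity and so does not answer the hypothesis stated in both documents. That conclusion rests on the text alone and is firm.

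The numerical consequence is uncertain. Over the assumed range (ρ 0.3-0.5, b 0.2-0.4 SD), the unadjusted difference is biased by 0.05-0.16 s⁻¹. False rejection is 7%-23%, against about 5% with AHI always included. When the effects oppose, a true 0.3 shrinks to 0.14-0.25. If either link is weak the effect is small, and if either is zero there is none. The direction of any bias cannot be told from the documents.

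The possible p<0.10 screen is a lesser problem. It matters mainly when the effects oppose, with estimates of 0.24-0.29 and power 3 to 12 points below the model that always includes AHI.

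**What to change.** - **Main Aim 2A analysis:** linear regression of PVT on arousal-threshold group (the planned median split) with baseline AHI always included. Fix the AHI scale in advance and name the sleep study that supplies it, since the protocol allows a laboratory or home study at the first overnight visit and plans a second polysomnogram. Report the t-test as supportive.
- **Covariate sentence:** rewrite it so that AHI's inclusion does not depend on the p<0.10 screen.
- **Power:** restate it for the adjusted model.
- **Related comparisons:** in Aim 3, include AHI the same way in the high versus low loop gain comparison of change that the SAP powers, but not in the within-person paired t-test. Hypothesis 2B carries the same severity wording, and the SAP's Aim 2 analysis paragraph gives no test for it; it needs the same term when one is written.
- **Alternative:** if the sponsor wants the unadjusted contrast, remove the equal-severity wording from the hypothesis in both documents.

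The operational cost is SAP wording, because AHI is already measured on everyone. The statistical cost is one degree of freedom and a 6%-19% rise in the variance of the group effect over the assumed range, before any reduction in residual variance. Power at N=60 is 0.57-0.68 adjusted against 0.63 unadjusted. Reaching 0.80 needs 80-102 people with OSA adjusted against 90 unadjusted.

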Statistical Analysis Plan: To test change over time after 3 months of PAP therapy in the PLWH+OSA group, we will compare endothelial dysfunction (EndoPAT) at baseline versus 3 months via a paired t-test. Based on Itzhaki and colleagues, we anticipate a mean endothelial function of 1.77 (SD 0.4) in those with untreated OSA, and that a delta of 0.3 represents a clinically important difference based on the effect size of treatment of OSA observed in our prior studies (Ref 127). Assuming a change in mean endothelial function of 0.5 in those with high LG induced OSA vs a change of just 0.2 in those with low LG OSA, we will have adequate power (beta >0.82) to detect this difference between the two groups (alpha = 0.05). As a sensitivity analysis, we will consider multiple regression models adjusting for additional covariates such as age, AHI, medications, mean sleep duration as assessed by actigraphy, and inflammation as assessed by CRP or IL-6 may be included in the modeling if significantly associated with outcome (p<0.10).

References

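### In Aims 2 and 3 the p<0.10 outcome screen can leave AHI, and weak or masking confounders, out of the only adjusted models; name the covariates in advance and keep them

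*SAP*

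**What the plan says.** The Aim 2A comparison is unadjusted: "We will evaluate if there is a difference in PVT in OSA participants with low vs high AT using a two-sample t-test". The groups come from an observed trait: "We will split the cohort of those with OSA into high and low arousal threshold at the median value for the group". The expected number is about 60: "Of the 120 PLWH studied in Aim 1, we believe that at least 60 will have OSA".

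Adjustment comes next, at lower rank: "As a sensitivity analysis, we will consider multiple regression models adjusting for additional covariates such as age, AHI, medications". The list continues with actigraphic sleep duration and inflammation (CRP or IL-6), and the sentence ends: "may be included in the modeling if significantly associated with outcome (p<0.10". The Aim 3 analysis paragraph repeats the clause after a paired t-test of baseline against 3 months.

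The Aim 2A hypothesis is conditional on severity: "low arousal threshold induced OSA yields worse neurocognitive dysfunction compared to equal severity OSA with high arousal threshold". Hypothesis 2B and the Aim 3 example carry the same condition, as do the protocol's Specific Aims (section 6).

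The Aim 1 regression uses nearly the same covariates and has no p-value condition.

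**The concern.** Arousal threshold and loop gain are measured, not randomised, so the endotype groups may differ in age, medication or AHI. A covariate confounds when it is related to both group and outcome. The p<0.10 rule examines only the outcome side, with the limited power of about 60 people. A covariate that is clearly unbalanced between groups but modestly related to the outcome can fail it.

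AHI matters most. The stated question holds severity constant, but no stratified or matched analysis is specified for Aims 2 and 3. AHI enters only through this list. If it misses p<0.10, no analysis addresses the hypothesis as written. The protocol's background (section 7) itself says that AHI is not strongly correlated with most relevant OSA co-morbidities, so a failed screen is plausible.

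The wording adds a second problem. It is permissive, and it does not say whether the screen is univariable or within the model. An analyst could settle both after seeing the data.

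**Working it through.** **Plan's own figures.** The SAP gives no figure for covariate retention or residual confounding. The planned Aim 2A effect sets the scale: "assuming a mean reciprocal reaction time of 3.9 seconds⁻¹ in those with low arousal threshold OSA and 4.2 seconds⁻¹" in the high group, SD 0.5, so 0.3/0.5 = 0.6 SD. With 30 against 30, two-sided power is Φ(0.6 × √(30/2) − 1.96) = Φ(0.364) = 0.64 (0.63 by noncentral t). The SAP's claim of more than 0.8 is not reproduced. That is a separate matter, but it is the baseline for the power figures below.

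**Step 1: chance of passing the screen.** Inputs are n = 60 (SAP, Aim 2) and p<0.10, assumed two-sided. By Fisher z, the chance is Φ(atanh(r)·√57 − 1.645) plus a negligible opposite tail. At r = 0.20: atanh = 0.2027, times 7.550 = 1.531, Φ(−0.114) ≈ 0.455, and with the opposite tail 46%.

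| Correlation with outcome | Kept |
|---|---|
| 0.10 | 20% |
| 0.15 | 31% |
| 0.20 | 46% |
| 0.25 | 61% |
| 0.30 | 76% |
| 0.40 | 94% |

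The 50% point is atanh(r) = 1.645/7.550 = 0.218, so r ≈ 0.21. With 54 or 45 people in the analysis it is about 0.23 or 0.25.

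**Step 2: bias left behind.** The documents give no association strengths, so these are assumptions. The simulation has 60 people, a trait split at its median, confounders correlated 0.4 in absolute value with the trait, and a coefficient of 0.2 on the outcome in SD units (1 SD = 0.5 s⁻¹). The screen is univariable except where noted.

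| Scenario | Screened model | Fixed covariates |
|---|---|---|
| One confounder, no true effect | bias 0.03 to 0.05 SD; type I error 5 to 7% over both readings of the screen | bias about 0; about 5% |
| One confounder opposing a 0.6 SD effect | kept about 20%; bias −0.09 SD (−0.045 s⁻¹) | bias about 0 |
| Three independent confounders opposing 0.6 SD | bias −0.25 SD (−0.125 s⁻¹); power 26% | bias about 0; power 52% |
| Three confounders related through the trait, opposing 0.6 SD | kept 36%; bias −0.16 SD; power 37% | bias about 0; power 56% |

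Against the planned 0.6 SD, −0.09 is 15% and −0.25 is 42%. The last figure needs strong confounding: three independent confounders at 0.4 explain 3 × 0.16 = 48% of the trait's variance.

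**Step 3: direction and reading of the screen.** With one confounder acting in the same direction as a true 0.6 SD effect and a coefficient of at least 0.2, the covariate is kept 64 to 99% of the time, and bias is at most 0.01 SD. Masking is worse because the endotype effect cancels the covariate's marginal association with the outcome, so the covariate fails a univariable screen. If p is taken from the model that already contains endotype, masking bias roughly halves: at coefficient 0.2, from −0.06 to −0.03 SD (trait correlation −0.3) and from −0.12 to −0.05 SD (−0.5).

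**The case against.** These are sensitivity analyses. The larger exposure to confounding is the unadjusted t-test, and even a screened model usually improves on it. With three independent confounders and no true effect, bias is 0.38 SD unadjusted and about 0.14 SD screened. That stands. It does not rescue the rule, because the adjusted models exist to check the t-test, and they do so poorly if they can omit the confounders.

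A reader might infer that true confounders are usually dropped and that the adjusted estimate therefore remains biased. The calculations do not support this. Covariates with r of 0.3 or more pass at least 76% of the time unless masked, and several scenarios leave almost no bias.

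A reader might also infer a badly inflated type I error. A rate near 13% under a univariable screen needs five independent confounders, each correlated 0.4 with the trait. These would explain 5 × 0.16 = 80% of its variance, and nothing in the documents suggests that. About 12% is reached with three confounders if p is taken from the full model. With one confounder the rate is 5 to 7%.

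Finally, the text is looser than a strict rule. It says covariates may enter, and its broken grammar allows a reading in which only inflammation is screened. On that reading AHI would be among the covariates to be considered, but the SAP still would not commit to including it.

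**Conclusion.** The point holds in limited form. As most naturally read, the SAP selects confounders by outcome p-value in about 60 people, in the only adjusted models for Aims 2 and 3, and AHI is on the screened list although the hypotheses are conditional on severity. The AHI problem follows from the text and needs no assumed number.

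The numerical harm depends on assumptions. It is small for one confounder with no true effect and material for confounders that mask a true effect. The simulated outcome was PVT. Nothing was computed for EndoPAT, the SAP gives no analysis paragraph for Hypothesis 2B, and it does not say that the Aim 3 regression contains an endotype term, though the hypothesis needs one. This is a cheap improvement to the sensitivity analyses; it does not by itself undermine the main tests.

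**What to change.** - Delete the p<0.10 clause in the Aim 2 and Aim 3 analysis paragraphs.
- Always include AHI in the endotype models.
- Name a short covariate set from the SAP's own list before analysis, with at least age and medications, and define how medications are coded. Enter it whatever its p-values. Record in advance whether sleep duration and CRP or IL-6 belong in it.
- State the endotype term in each model, and report its coefficient and 95% confidence interval beside the t-test.

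The cost is SAP wording, a few degrees of freedom and some precision. With three covariates strongly related to the endotype, the standard error is about 0.30 against 0.26 SD (0.30/0.26 = 1.15, about 15% wider). With five it is about 0.34 against 0.27 SD, which is a reason to keep the set short.

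### Aim 3 names a paired t-test of overall EndoPAT change, but its stated power belongs to a high- versus low-loop-gain comparison for which the SAP gives no test and no split

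*SAP*

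**What the plan says.** The SAP opens Aim 3 with a general question: does three months of PAP change OSA manifestations in people with HIV and OSA? It then states a hypothesis, that "endotype underlying OSA will be predictive of the specific clinical improvements seen in adherent users of PAP therapy". The worked example is that participants with high loop gain should show the greatest improvement in endothelial dysfunction, "compared to other OSA patients with similar disease severity as measured by AHI".

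In the Statistical Analysis Plan paragraph for Aim 3, the only test named is in the sentence "we will compare endothelial dysfunction (EndoPAT) at baseline versus 3 months via a paired t-test". The power argument follows: "Assuming a change in mean endothelial function of 0.5 in those with high LG induced OSA vs a change of just 0.2" in low loop gain, and then "we will have adequate power (beta >0.82) to detect this difference between the two groups (alpha = 0.05". The only SD given is 0.4, attached to a mean EndoPAT of 1.77 in untreated OSA. The paragraph closes with sensitivity regressions whose covariates "may be included in the modeling if significantly associated with outcome (p<0.10").

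For arousal threshold in Aim 2 the SAP is explicit on both elements. The split: "We will split the cohort of those with OSA into high and low arousal threshold at the median value for the group". The test: "We will evaluate if there is a difference in PVT in OSA participants with low vs high AT using a two-sample t-test". Neither the SAP nor the protocol gives the corresponding split or test for loop gain.

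**The concern.** The paired t-test pools all loop-gain values. A clear result from it would say that EndoPAT changed, and nothing about whether loop gain predicts the change. The plan therefore powers one contrast and names a test of another.

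Followed as written, the SAP yields a named result for overall change and none for the endotype hypothesis. That hypothesis matters to the study: that endotype influences response to treatment is part of the third overall hypothesis at the end of the protocol's background section.

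A two-sample comparison of change is the natural way to fill the gap, but three choices would remain open once data are in hand: where to cut loop gain, whether AHI is in the model, and whether baseline EndoPAT is in the model. The last is not cosmetic. Hypothesis 2B expects worse endothelial function with high loop gain at baseline. If that is so, comparisons of change with and without baseline adjustment answer different questions.

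**Working it through.** **Inputs from the SAP.** Changes of 0.5 and 0.2, so a difference of 0.3. SD 0.4, given for untreated level. Alpha 0.05. About 60 participants with OSA (Aim 1 expects 60; Aim 2 says at least 60).

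**Assumptions here.** Two-sided testing, since sidedness is not stated for this comparison. Equal groups of 30, since no loop-gain split is stated.

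**1. Reproduce the stated power.** Two-group comparison of change, n per group, SD of change s:

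noncentrality = 0.3 / (s × √(2/n)) = 0.3 / (0.4 × √(2/30)) = 2.905.

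Normal approximation: Φ(2.905 − 1.960) = 0.828. Exact noncentral t on 58 df: 0.815. The stated >0.82 is recovered.

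**2. Is it the power of the named test?** The mean change over two equal groups is (0.5 + 0.2)/2 = 0.35. For a paired t-test on 60, noncentrality = 0.35 / (0.4/√60) = 6.78, and power exceeds 0.999. With SD of change 0.566 it is 0.997. So the stated figure is not the power of the paired test.

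**3. Does the unstated split matter?** Same inputs, 60 participants, exact t: 30/30 gives 0.815, 20/40 gives 0.768, 15/45 gives 0.696.

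**4. Number analysed.** Exact t, SD of change 0.4, equal groups:

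| Per group | Power |
|---|---|
| 30 | 0.815 |
| 29 | 0.801 |
| 27 | 0.772 |
| 24 | 0.720 |
| 20 | 0.637 |

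The smallest equal groups reaching 80% are 29 each, which is 58 of the expected 60. The row for 27 applies to Aim 3 the 10% attrition that the SAP allows for Aim 1 (60 × 0.9 = 54). The SAP states no loss for the three-month PAP phase, so this row and the two below it are assumptions.

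**5. SD of change.** If 0.4 is the SD at each visit and r is the correlation between visits, SD of change = 0.4 × √(2(1 − r)). At 30/30:

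| r (assumed) | SD of change | Power |
|---|---|---|
| 0 | 0.566 | 0.52 |
| 0.3 | 0.473 | 0.68 |
| 0.5 | 0.400 | 0.81 |
| 0.7 | 0.310 | 0.96 |

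Using 0.4 as the SD of change is equivalent to r = 0.5. The documents give no r.

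**6. With AHI in the model.** Change regressed on loop-gain group and AHI, SD of change 0.4, 12,000 simulations, assuming that AHI has no effect on change given loop gain. At 30/30, power is 0.81, 0.77 and 0.69 for AHI/loop-gain-group correlations of 0, 0.3 and 0.5. As a check, the noncentrality in step 1 shrinks by √(1 − correlation²), to 2.905, 2.771 and 2.516. These correlations are assumptions.

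**The case against.** The strongest reply is that the missing test can be recovered. The power sentence gives the outcome (change), the groups, the difference and alpha. Its value reproduces at 30/30, and a median split is the only endotype rule in the SAP. Most of this stands: a two-sample comparison of change is the natural reading. But the cut-point and the handling of AHI and baseline are not settled by it, and the SAP did write out split and test for arousal threshold.

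It is also fair that the paired t-test answers Aim 3's opening question, and that the loop-gain contrast is introduced as an example. A reader might infer that the paired test is the wrong test and should go. The documents do not support that; it is right for overall change.

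A reader might take loop gain's absence from the sensitivity covariates as a sign that it was left out of the model. That does not follow. The list is of additional covariates, and the matching Aim 2A list omits arousal threshold, which is plainly the exposure there.

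A reader might also infer that AHI enters only if p<0.10. The sentence is grammatically broken: the rule can be read as covering the whole list, including AHI, or only the inflammation markers. What can be said is that AHI's inclusion is not assured.

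Finally, the power figures can move upward. If AHI explained 10% of the within-group variance in change (an assumption), the AHI-adjusted figures at 30/30 would be about 0.85, 0.82 and 0.74 for the same three correlations. If more than 60 have OSA, power also rises: 36 per group, for illustration, gives 0.88.

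**Conclusion.** The point holds. The SAP's only named Aim 3 test cannot address the endotype hypothesis, and the stated power belongs to a comparison with no named test and no loop-gain split. These are matters of text and rest on no assumption.

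The power figure is not an arithmetic error, and it would be too strong to call it wrong. It is correct for 30/30 with SD of change 0.4. What it lacks is margin: it needs nearly all of the expected 60 analysed, for a hypothesis about adherent users, and it uses a level SD as an SD of change. The range of 0.64 to 0.77 for 20 to 27 per group rests on assumed retention. The range of 0.52 to 0.96 rests on assumed visit correlations from 0 to 0.7. The AHI-adjusted range of 0.69 to 0.81 rests on assumed correlations and on AHI having no effect on change.

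This should be fixed before analysis. The Aim 1 FACIT-F outcome and the test of overall change are unaffected.

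**What to change.** Keep the paired t-test for overall change, and add to the Aim 3 analysis text:

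- **A named test of the endotype hypothesis.** Change in EndoPAT from baseline to three months, compared between high and low loop gain in a linear model that always includes AHI, because the hypothesis compares patients of similar AHI. Report the loop-gain difference with its 95% CI.
- **The split.** The median loop gain of the participants analysed. This carries over the SAP's own arousal-threshold rule and keeps the groups equal.
- **The analysis sets.** All treated participants with three-month data, and also adherent users by a definition fixed in advance from the PAP download that the protocol already collects at Daytime Visit #2.
- **Optional sensitivity analyses.** Loop gain as a continuous term, and the model with baseline EndoPAT added, labelled as answering a different question.
- **Restated power.** For this test, with a justified SD of change and the number expected to be analysed.

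The cost is a few sentences and one more regression; no new data are needed. The stated power will probably look less favourable than >0.82. A median split also gives up power if change is linear in loop gain: in simulation with 60 participants and AHI unrelated to loop gain, about 0.79 against 0.94 for a continuous term. It is kept as the main contrast because it is the one the SAP powers.
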